10.4 Missing Data

Several procedures will be used to conduct data analysis when data for either outcomes or covariates are missing. The first step will be to assess the extent and pattern of missing data. If data are missing for only a few cases, then data analysis will be conducted only on study participants with complete data. However, when such a strategy would result in loss of data from a substantial proportion of participants, or if this approach would lead to biased or inaccurate results, then some form of imputation will be performed. The form of imputation used will depend on the nature of the data that are missing. For example, data that are collected repeatedly might be imputed using the “last value carried forward” method; and in some instances, interpolation between neighboring points might also be used.

When the primary endpoint is missing, one data analysis will be conducted using only cases with the endpoint. Subsequent analysis will be done where missing endpoints are imputed. Hot-deck imputation or regression imputation may also be used in this context.

HUMAN SUBJECTS

This study will be conducted in compliance with the protocol, ICH Good Clinical Practice (GCP) guidelines, and 45 CFR Part 46.

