10.3.4 Secondary Analyses for RCT of YouTHrive

As a secondary aim, we will investigate whether there is greater benefit from the YT intervention for substance-using participants compared with nonsubstance-using participants. We will use the same modeling approach described above to address this aim. First, we will examine the association between the intervention and viral detection separately among those who did and did not self-report current (since the last visit) substance use (i.e., yes/no for problematic alcohol use and/or illicit drug use). Second, to formally test whether there is an interaction between intervention arm and substance use, the models described above will be refit including an interaction term between substance use and intervention arm. Interactions will be evaluated on the additive scale. We will carefully examine the distribution of potential confounders of the substance use and VL association and adjust for them as necessary. As mentioned previously, we will adjust for covariates where appropriate.

The models described use logistic regression to model the outcomes. We will use estimates from these models to report prevalence differences and ratios. However, alternative (log-linear and Poisson) models may be explored to allow easy interpretation of parameters in the presence of common outcomes. In the event of loss-to-follow-up among study participants, we will perform sensitivity analyses of an alternative outcome. We will define an additional outcome where a failure is defined as either detectable VL or loss-to-follow-up. The analyses described above will be repeated with this alternative outcome. All of the models mentioned above can be modified to accommodate missing values in the outcome or covariates over time without dropping participants. Although attempts will be made to limit missing data, in the event that this occurs, we will carefully examine patterns of missingness. Multiple imputation will be implemented, as needed, to deal with missing covariate data.

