Finally, we will examine models that include covariates that quantify the degree of site usage and which components were used. The additional outcome of self-reported ART adherence will be examined. The outcome will be defined as the percentage of ART taken in the past 30 days. Differences in this proportion by study arm will be evaluated using the same approach as described above. To explore the effects of the YT intervention on the intermediate theory-based processes of change, we will use the IMB-AAQ informational and motivational scales, adherence self-efficacy, and social support measures at each time point. These scales will be included as outcome variables in linear regression models to test the main effect of intervention arm.

Note: Any deviations from the analysis plans outlined above or in the sections that follow will be documented and justified in the Statistical Analysis Plan developed for this protocol.

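### Section 10.4 imputes missing primary endpoints by hot-deck or regression with no variance rule, and a few endpoints may also be lost in the YT arm only

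*Combined protocol and SAP*

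**What the plan says.** The primary test in 10.3.3 is a chi-square comparison of undetectable VL at 5 months. For a missing primary endpoint, 10.4 gives two steps. First, "one data analysis will be conducted using only cases with the endpoint". Then, "Subsequent analysis will be done where missing endpoints are imputed". The paragraph adds: "Hot-deck imputation or regression imputation may also be used in this context". It does not say whether values are drawn once or many times, whether donors or models stay within arm, or how the standard error reflects the imputation.

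Related text:

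- The general part of 10.4, which covers outcomes as well as covariates, gives as an example that "data that are collected repeatedly might be imputed using the" carry-forward method, and also mentions interpolation. Whether either reaches the 5-month VL is not stated.
- 10.3.4 says its models "can be modified to accommodate missing values in the outcome or covariates over time without dropping participants", without saying how. VL is measured only at enrollment and 5 months (10.1.3), so a logistic model of the 5-month VL has no later value to use.
- 10.3.4 also says: "Multiple imputation will be implemented, as needed, to deal with missing covariate data".
- 10.3.4 plans a sensitivity outcome in which "a failure is defined as either detectable VL or loss-to-follow-up". It does not say whether withdrawal from the study counts as loss to follow-up.
- The closing note of 10.3.4 says that deviations "will be documented and justified in the Statistical Analysis Plan developed for this protocol".

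On withdrawal, 8.3 takes a participant out of the study at the third hostile offense, or sooner in extreme cases, and 11.3.1 agrees. Section 5.4.3 notes that the control pages are not interactive. Section 8.4 ends medical record abstraction at discontinuation, although 6.3.3 lists the record as a source of the 5-month VL. Section 8.4 also allows re-enrolment case by case.

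**The concern.** The imputed analysis is there to show whether the complete-case result depends on who was measured. It can do so only if its standard error allows for the imputed values being uncertain, and if the imputation itself neither creates nor erases a difference between arms. The wording of 10.4 admits choices that fail in opposite directions: one is too liberal, another dilutes the effect. Nothing fixes the choice before results are seen. Missing endpoints are to be expected, since 10.2.3 assumes about 85% follow-up and reports that COVID made VL hard to obtain.

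The withdrawal route is a separate matter. Losses that can arise in only one arm are not balanced by randomisation.

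**Working it through.** **Missing share.** The power statement in 10.2.3 reproduces: (1.960 + 0.842) × 43 × √(2/120) = 15.55, stated as 15.6 points. It concerns self-reported adherence, so it serves here only as the source of the follow-up share. Follow-up of 85% implies 15% missing. The 20% is an assumption: it is what 240 analysed out of the target of 300 would give, but 10.2.3 does not pair those numbers (240/0.85 = 282). The 30% is an assumed upper value.

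**Complete cases.** With equal suppression in both arms (50%, 60% or 70% assumed) and missingness completely at random, simulated type I error was 4.5–5.3%.

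**One within-arm hot-deck draw, analysed as observed.** With N = 150 per arm and a fraction f missing, the true variance of an arm's proportion is about s²[1/((1−f)N) + f/N], while the reported variance is s²/N. The ratio is 1/(1−f) + f, and type I error is 2[1 − Φ(1.96/√ratio)].

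| f | Variance ratio | SE ratio | Type I error |
|---|---|---|---|
| 0.15 | 1.33 | 1.152 | 8.9% |
| 0.20 | 1.45 | 1.204 | 10.4% |
| 0.30 | 1.73 | 1.315 | 13.6% |

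Simulation gave 8.9–9.6% at 15% missing and 10.5–11.1% at 20%.

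**Regression.** Section 10.4 does not say whether a random draw or a fitted value is meant. One random draw by arm on baseline VL gave 8.0–8.8% and 9.3–10.4% at 15% and 20% missing. Within-arm fitted proportions followed by a chi-square test gave 7.0–7.1% and 8.0%.

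**Pooled donors or carried-forward baseline VL.** Imputed values then have the same expectation in both arms, so a true difference d becomes (1−f)d. For an assumed d = 15 points this is 12.8, 12.0 and 10.5 points at 15%, 20% and 30% missing. Type I error stays near 5% (5.0–5.7%).

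**Multiple imputation by arm (20 imputations, Rubin's rules).** Type I error was 5.0–5.3% at 15–20% missing, and 14.9–15.0 of the 15 points were recovered. Power was 73–75% at 15% missing and 70–72% at 20%, against 73% and 70% for complete cases.

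**Bias when missingness depends on baseline VL (assumed scenario).** There is no true effect, and 60% are suppressed at baseline. Suppression at 5 months is 80% or 30% by baseline status. In YT only, those unsuppressed at baseline have 3 times the odds of a missing 5-month VL, with 20% missing overall.

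- YT missing shares are 12.9% (suppressed) and 30.7% (unsuppressed), so the suppressed share among those observed is 0.6 × 0.871/0.8 = 0.653.
- Complete-case bias is (0.65325 − 0.600) × (0.80 − 0.30) = 2.7 points, with simulated type I error of 7.3%. With a weaker predictor (70% v 45%) the figures are 1.3 points and 5.5%.
- Multiple imputation leaves 0.1 points if baseline VL is fully observed. If baseline VL is itself missing at random in an assumed 15–30%, joint imputation leaves 0.4–0.8 points. That case is plausible: 10.2.3 describes VL collection at both time points as difficult, and the definitions of enrolment in 5.1, 5.4.3 and 6.2 do not depend on a VL result.

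**YT-only withdrawals.** Each one leaves the YT rate uncertain by at most 1/150 = 0.67 points. The standard error of the difference at 60% suppression is √(2 × 0.6 × 0.4/150) = 5.7 points with complete data, and 6.1 and 6.3 points at 15% and 20% missing. The documents give no count.

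**The case against.** The wording on hot-deck and regression is permissive, and nowhere is a single imputation stated. A valid variance is left unspecified, not ruled out. A reader might infer that the trial's own type I error is 9–10%. The documents do not support that: the complete-case analysis comes first, the imputed analysis follows it, and 10.3.4 adds a missing-equals-failure analysis. The inflated rates belong to one possible version of a sensitivity analysis.

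Carry-forward is only a general example, and interpolation cannot serve a final time point. The YT-only odds ratio of 3 is an assumption with no source in the documents, and under random missingness multiple imputation adds little power. A separate Statistical Analysis Plan may settle the method.

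On withdrawals, a reader might infer a material bias in a known direction. That is not supported either. Removal follows a reminder and a warning except in extreme cases, re-enrolment is possible, the general harm and non-compliance criteria in 8.4 apply to both arms, and numbers are probably small.

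These limits are accepted. What stands is that imputation of the endpoint is a firm commitment, that hot-deck and regression are the only methods named specifically for it, and that multiple imputation is reserved for covariates. The note about the Statistical Analysis Plan promises only to record deviations, so it does not fill the gap.

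**Conclusion.** The point holds as a weakness of the planned follow-on analysis, worth correcting before unblinded results are seen. If one within-arm hot-deck data set is analysed as observed, the check runs at about 9% type I error with 15% missing and about 10% with an assumed 20%. Pooled donors or carry-forward instead remove about 15–20% of any true difference. These figures assume 150 per arm and missingness completely at random. The primary chi-square is not inflated if missingness works alike in both arms.

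Multiple imputation by arm gives valid error rates under missing at random. It reduces bias when missingness depends on baseline VL, but it would be too strong to say that it removes that bias, because baseline VL may also be missing. Its predictors beyond baseline VL were not simulated.

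The withdrawal route is real but minor: at most 0.67 points per participant, with number and direction unknown.

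This point takes the VL endpoint of 10.3.3 as primary. Section 10.2.3 calls self-reported adherence primary, and that conflict should be settled as a separate matter.

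**What to change.** In 10.4:

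- Replace hot-deck or regression imputation of the 5-month VL with multiple imputation by arm, combined by Rubin's rules. Use baseline VL (itself imputed where missing), city, other collected baseline predictors such as age, substance use and adherence, and 5-month self-reported adherence where the survey was completed.
- State that carry-forward and interpolation do not apply to the 5-month VL.
- Keep the complete-case and missing-equals-failure analyses, and say that withdrawal from the study counts as loss to follow-up in the latter.
- Add a delta (missing-not-at-random) sensitivity analysis with shifts set by arm.

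In 8.3 and 8.4, leave the site-removal rule unchanged. Reconcile the two sections so that removal from the website does not by itself end 5-month outcome collection where consent stands and no other discontinuation criterion applies. Analyse these participants as randomised.

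The cost is modest programming and small changes to protocol and consent wording, with no new visits or measures.

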11.1 Participants' Confidentiality

All laboratory specimens, questionnaires, evaluation forms, reports, transcripts, and other records will be identified by a coded number and participant code to maintain participant confidentiality. All records with personally-identifying information will be kept in a locked file cabinet in a limited secure access area at each SRV site. All computer entry and networking programs will be done with coded numbers only. Clinical information will not be released without written permission of the participant, except as necessary for monitoring by the MC or NICHD.

Every effort will be made to ensure that study participants are protected from risks. The main risk specific to the role of the AC is breach of confidentiality.

Breach of Confidentiality: A potential risk to participants is violation of confidentiality. We will take the utmost caution to protect the confidentiality of all responses. We will minimize this risk by maintaining confidentiality and discretion throughout all iTech research procedures and data management and analysis.

Participants may be concerned about the security of their data, particularly since it is collected and stored electronically. The AC has significant experience developing security protocols for Internet-based studies, and we will take a variety of steps to ensure participant security, including using a dedicated server behind a firewall, encryption of data, separation of identifiers from responses, and password-protected access to data. Therefore, we believe that this risk will be minimal. All of the apps and websites included in the iTech have features to ensure app security and privacy.

For the YT intervention in Aim 3 - RCT, participants will create a unique username that does not contain any identifying information but will be their social media handle on the YT website. Intervention participants will have the option to upload a profile picture in keeping with the site guidelines or select an anonymous avatar to represent themselves on the site. Participants are told at the enrollment visit and in multiple places on the YT website that it is a violation of community guidelines to reveal identifying information including name, address, phone number, email address, social media handles, places of employment, or locations to meet for personal or business use. Participants will not be able to privately communicate with each other on the YT website - all conversations are viewable on the main feed. Trained research staff at the San Diego State University (SDSU) will monitor the website daily to ensure violations to privacy, even through self-disclosure, are addressed. Participants will also be able to flag others' postings if they feel they have violated community guidelines. The YT website will use an "https" URL and entry into the website that is also password-protected.

11.2 Certificate of Confidentiality

This research specifically targets a vulnerable population, children - YMSM ages 15-17. We will take every available step to minimize the risk of identifying/linking data being subpoenaed, stolen, or inadvertently released. First, the iTech will request a Certificate of Confidentiality from the NIH. Second, all research staff members are required to complete ethical clearance certification regarding protection of human subjects through their relevant IRBs. Third, all

studies will have documented procedures to safeguard against the risk of the linking information being stolen by keeping such information in locked spaces to which only essential study personnel who have completed CITI certification for human subjects research ethics training (<http://citiprogram.org>) will have access.

A Certificate of Confidentiality for the iTech will be sought prior to enrolling participants. As noted on the NIH website (<http://grants.nih.gov/grants/policy/COC/faqs.htm#187>), a Certificate of Confidentiality will help the research team "...avoid compelled 'involuntary disclosure' (e.g., subpoenas) of names and other identifying information about any individual who participates as a research subject (i.e., about whom the investigator maintains identifying information) during any time the Certificate is in effect." We have applied for and received Certificates of Confidentiality for other NIH-funded research projects, and given the sensitive nature of the data collected for this project, do not foresee difficulty securing one for this study.

11.3 Risks and Benefits

11.3.1 Risks

Risks to participants in this research study may include:

By misspelling a web address or "surfing" the net, some individuals may unintentionally go to the study website. We deem this unlikely as we will use the prefix "https:" to prohibit persons from coincidentally viewing the site. Nonetheless, if someone were to mistakenly view the study website home page, we anticipate that the information contained on the homepage will be benign to viewers.

Potential participants or participants enrolled in the study may have concerns about others finding out about their HIV status or other personal behavior (e.g., sexual behavior or substance use). We anticipate that the likelihood of this occurring is high given that a major feature of the intervention is for participants to network with one another and that eligibility for enrollment in the study requires participants to identify as a HIV-positive. We anticipate these concerns to be even higher for focus group participants as well, since they will be meeting in-person with other YLWH. Subjects will be informed of the inclusion criteria and general questions that will be asked during focus groups during the recruitment period. Since subjects will be recruited directly within clinics, they will have the opportunity to discuss with clinic staff whether they feel comfortable being a part of such discussions. Clear consent procedures and an introduction from the PI will also give opportunities for subjects to withdraw if they no longer feel comfortable participating in focus group discussions. For those in the RCT, subjects will be informed during the consent process of the basic features of the intervention and those who are not comfortable interacting with other HIV-positive persons will be encouraged to not participate in the study. Those who do enroll will be given the option of utilizing intervention features with which they feel comfortable, although utilization of all features will be encouraged.

The measurements that are involved in this study require venipuncture and self-administered finger pricks to collect blood samples. This procedure may cause local discomfort, bleeding, or bruising; rarely small clot or infection can occur at the blood draw site. This measurement should not be considered greater than minimal risk in and of itself given its routine use in general health care delivery.

To minimize the risk of participants feeling uncomfortable about answering personal questions, we will use CASI methods for the study's surveys. In CASI, participants read survey questions on a laptop computer or mobile phone and use a combination of mouse click and keyboard/touchscreen entry to input the answers themselves. Study staff may be available to assist participants with questions or technical difficulties on the CASI. Participants will also be able to refuse to answer any question that makes them uncomfortable.

Participants may receive hostile communications or incorrect information from other participants during the course of the intervention. It is possible that some participants may respond aggressively or with hostility to other participants. Likewise, although well-intended, participants may provide inaccurate information about adherence or its risk factors to other participants by interactions through the website message boards/social networking wall. The YT intervention website includes a clear section on Community Guidelines and will be monitored daily by research staff. Users have the option to “flag” objectionable content. We have protocols in place for addressing hostile interaction in the site up to and including termination of participation in the study.

To minimize risks to confidentiality, we will secure study data with all appropriate physical, electronic, and operational protections. Data will be stored in a physically secure environment. All data files will have encryption and strong password protection. Any identifiable data will either be stored on Emory University's secure servers or will be on fully encrypted laptops. CASI surveys and online eligibility screening will take place on an encrypted commercial survey website, Alchemer. This site has been used by the investigators for thousands of online surveys with MSM with no data security breaches. Access to data will be on a role-based standard; only those study staff who require access to each type of data to complete their study-related roles will be allowed access. All study staff will be trained in security and confidentiality procedures, and will sign a confidentiality agreement before receiving access to any participant data.

We will also develop procedures to minimize indirect disclosure that a participant is participating in an HIV-related research study, or a study that enrolls MSM. For each mode of contact information, we will ask specifically whether anyone else potentially has access to that mode of communication, and if it is acceptable to leave a non-specific message about participation in a health study. No study-related messages will ever mention HIV prevention or the nature of the research study. Additionally, all scripts for email, text message, and telephone contact with participants will be reviewed and approved by the UNC IRB before being used for contact with participants.

We use SSL encryption for transfers of information online, and Alchemer has a business partner HIPAA agreement with Emory. Alchemer's servers are HIPAA compliant.

The AC will use Dedoose software to perform all qualitative analyses. Dedoose is a web-based application for organizing and analyzing textual, audio, and video data (qualitative) along with outstanding functionality for their integration with survey, test score, ratings, and demographic data (quantitative). Dedoose employs the highest levels of data encryption available for a web application in all data storage, back up, and transmission. Dedoose allows for project specific encryption feature. When using this feature, only [name] or her designee will hold the additional encryption key needed to be entered in order to view the project. This gives [name] exclusive control over who can view the project under any circumstances.

In addition to a Certificate of Confidentiality, we will protect participants in the following ways (which correspond to the potential risks described earlier):

1. Breach of confidentiality. We will take every precaution to minimize risks to study participants. All AC research staff members are required to complete ethical clearance certification regarding protection of human subjects through UNC-CH or Emory University. We also have a strong data and safety monitoring plan in place to protect participants. Adverse events will be reported to the UNC-CH and Emory IRBs, individual research PI institutional IRBs, and SRV site-specific IRBs per each institution's IRB reporting requirements using Adverse Event Reporting Forms created by the AC. When possible, reports will be sent within 24 hours of notification by the PIs. Annual updates on enrollment and retention will also be sent to the IRBs.

All data collection will take place in secure and supervised clinical settings. All study personnel have completed training and received certification in Human Subjects Research Protection (CITI Program) and HIPAA regulations. They will continue to renew this training in compliance with institutional policies.

